CSF PGRN Concentrations: A statistically significant increase in CSF PGRN levels (compared to baseline) was seen at both post-dose time points for each of these 3 cohorts (Day 2 and Day 13). The maximum increase in CSF PGRN was observed 12 days after dosing: 1.57 times for 15 mg/kg, 1.84 times for 30 mg/kg, and 2.11 times for 60 mg/kg compared to baseline. No statistically different changes in CSF PGRN levels have been observed in subjects that received placebo. In the 60 mg/kg expansion cohort, 24 days after dosing, the PGRN level was increased 1.83-fold over baseline and 42 days after dosing the PGRN level was increased 1.23-fold over baseline. Coefficients of variation were in the range of 20% to 40% for the 30 mg/kg and 60 mg/kg cohorts over the cited sampling period.

Safety: AL001 was generally safe and well tolerated through the highest dose assessed (60 mg/kg), without dose-limiting toxicities or apparent trends in adverse events (AEs).

Part 2, Patients with Asymptomatic FTD-*GRN* or Symptomatic FTD-*GRN*

The second part of the study was conducted in two cohorts: the first cohort assessed safety, PK, and PD after a single-dose of AL001 in asymptomatic carriers of a loss-of-function *GRN* mutation causative of FTD (asymptomatic FTD-*GRN*); while the second cohort assessed safety,

PK, and PD after repetitive dosing in symptomatic FTD carriers of a loss-of-function *GRN* mutation (symptomatic FTD-*GRN*). A total of 6 asymptomatic FTD-*GRN* participants and 8 symptomatic FTD-*GRN* participants were enrolled and completed dosing in the second portion of the study. Asymptomatic FTD-*GRN* participants were administered a single IV dose of AL001 at 60 mg/kg and symptomatic FTD-*GRN* participants were administered 3 doses of IV AL001 30 mg/kg, q2w.

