Plasma PGRN Concentrations: Consistent with the literature (Meeter 2016), both the asymptomatic FTD-*GRN* cohort (N = 5 who received 60 mg/kg) and the symptomatic FTD-*GRN* cohort (N = 8) had substantially lower baseline plasma PGRN concentrations than HV cohorts (1 asymptomatic participant was incorrectly dosed and is not included in the summary pharmacodynamic analyses). Mean baseline plasma PGRN concentration for the asymptomatic FTD-*GRN* cohort was 32.6 ng/mL (standard deviation [SD] of 13.6); for the symptomatic FTD-*GRN* cohort, mean baseline plasma PGRN concentration was 31.7 ng/mL (SD of 12.7). Treatment of the asymptomatic FTD-*GRN* cohort with a SD of 60 mg/kg AL001 resulted in an increase of plasma PGRN to approximately the baseline level of HV for 24 days (median concentrations of 118 to 124 ng/mL at Day 6 through Day 30 of the study). Treatment of the symptomatic FTD-*GRN* cohort with 3 doses of 30 mg/kg AL001 over a 4-week period resulted in an increase of plasma PGRN to at least 80% of the baseline level of HV for approximately 49 days, beginning 7 days after the first dose (median concentrations of 93.7 to 97.6 ng/mL at Day 8 through Day 57 of the study).

CSF PGRN Concentrations: Parallel to the results observed for plasma concentrations of PGRN, both the asymptomatic FTD-*GRN* cohort (N = 5 who received 60 mg/kg) and the symptomatic FTD-*GRN* cohort (N = 8) had substantially lower baseline PGRN concentrations in CSF than HV cohorts (mean of 1.67 ng/mL for the asymptomatic FTD-*GRN* cohort, 1.82 ng/mL for the symptomatic FTD-*GRN* cohort; approximately 55 to 58% of the HV mean of 3.1 ng/mL). Treatment of the asymptomatic FTD-*GRN* cohort with a single-dose of 60 mg/kg AL001 resulted in an increase of PGRN in CSF to 3.76 ng/mL, approximately 1.2 times the baseline level of HV, assessed 12 days after dosing. Treatment of the symptomatic FTD-*GRN* cohort with 3 doses of 30 mg/kg AL001 over a 4-week period resulted in an increase of PGRN in CSF to 3.76 ng/mL, approximately 1.2 times the baseline level of HV, assessed 28 days after the third dose of 30 mg/kg AL001 (57 days after the initial dose).

Safety: There were no deaths, no AL001-related serious adverse events (SAE)s, and no dose-limiting AEs. AEs have been predominantly mild to moderate in severity.

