3. INVESTIGATIONAL PLAN

3.1. Study Design

This is a Phase 2, multicenter, open-label study evaluating the safety, tolerability, PK, PD, and effect on COAs of AL001 administered intravenously (60 mg/kg, q4w) in asymptomatic and symptomatic carriers of loss-of-function *GRN* mutations causative of FTD and in symptomatic carriers of *C9orf72* hexanucleotide repeat expansion mutations causative of FTD. The study has two parts: A phase 2 open-label treatment period (Part 1), followed by an optional open-label extension (OLE) period (Part 2).

Part 1 is a 96-week evaluation of the safety, tolerability, PK, PD, and clinical effect of AL001 administered intravenously (60 mg/kg, every 4 weeks [q4w]), for a total of 25 doses (96-week dosing period), in asymptomatic and symptomatic carriers of loss-of-function *GRN* mutations causative of FTD, and in symptomatic carriers of *C9orf72* hexanucleotide repeat expansion mutations causative of FTD.

Part 2 is an optional OLE for eligible participants who have completed the 96-week Part 1 treatment period. The OLE period will evaluate the long-term safety and tolerability of AL001 administered at the same dose and regimen as Part 1 (60 mg/kg, q4w), for up to a total of 25 doses (96-week optional OLE period).

Part 1 (Treatment Period):

Two cohorts will be enrolled in Part 1: a *GRN* Cohort and a *C9orf72* Cohort. Both cohorts will enroll symptomatic participants with FTD; in addition, asymptomatic participants may enroll into the *GRN* Cohort, but only if they participated in the Phase 1 AL001-1 study (described in [Section 1.2.2](#)). Both asymptomatic and symptomatic carriers of a *GRN* mutation who participated in Study AL001-1 may enroll into the *GRN* Cohort if they completed dosing, the required follow-up portion of Study AL001-1 (further details are provided in [Section 4.1.1](#)), did not experience AEs that would indicate that continued dosing with AL001 would be unsafe, and meet the inclusion/exclusion criteria of Part 1 of Study AL001-2. In addition, new participants who are symptomatic carriers of a *GRN* mutation will be enrolled into the *GRN* Cohort. In total, up to 20 participants will be enrolled into the *GRN* Cohort (asymptomatic and symptomatic participants). Up to 20 new symptomatic carriers of a *C9orf72* hexanucleotide repeat expansion mutation will be enrolled into the *C9orf72* Cohort. An overview of the study schema is presented in [Figure 1](#).

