4.1.1. Inclusion Criteria – Part 1 (Treatment Period)

Prospective participants must meet all of the following criteria during the pre-study evaluation in order to be eligible to enroll in the study:

Part 1 (Treatment Period) Participant Category Inclusion Criteria:

1. Prospective participant meets all of the following criteria specific to their applicable participant category:

Participant Category 1: *GRN* Mutation Carriers, Symptomatic, from AL001-1

- Completed Study AL001-1 through the Day 57 visit and did not experience AEs that the investigator deems would prevent safe participation in Study AL001-2.
 - All previous participants in the AL001-1 study must be rescreened and meet all inclusion/exclusion criteria applicable to this study.
- Meets 1 or more of the 6 behavioral/cognitive symptoms required for a diagnosis of possible behavioral variant frontotemporal dementia (bvFTD; [Rascovsky 2011](#)), or has a diagnosis of PPA ([Gorno-Tempini 2011](#)).

Participant Category 2: *GRN* Mutation Carriers, Asymptomatic, from AL001-1

- Prospective participant completed Study AL001-1 through the Day 43 visit and did not experience AEs that the investigator deems would prevent safe participation in Study AL001-2.
 - All previous participants in the AL001-1 study must be rescreened and meet all inclusion/exclusion criteria applicable to this study. If a participant becomes symptomatic during or after Study AL001-1, they will be screened under Category 3 (symptomatic).

Participant Category 3: GRN Mutation Carriers, Symptomatic, New

- Is a carrier of a loss-of-function *GRN* mutation causative of FTD and knows their mutation status.
- Has a CDR® plus NACC FTLD global score of 0.5, 1, or 2; and 1 or more of the 6 behavioral/cognitive symptoms required for a diagnosis of possible bvFTD ([Rascovsky 2011](#)), or a diagnosis of PPA ([Gorno-Tempini 2011](#)).

Participant Category 4: C9orf72 Mutation Carriers, Symptomatic, New

- Is a carrier of a hexanucleotide repeat expansion *C9orf72* mutation causative of FTD and knows their mutation status.
- Has a CDR® plus NACC FTLD global score of 0.5, 1, or 2; and 1 or more of the 6 behavioral/cognitive symptoms required for a diagnosis of possible bvFTD ([Rascovsky 2011](#)), or a diagnosis of PPA ([Gorno-Tempini 2011](#)).

Part 1 (Treatment Period) General Inclusion Criteria:

2. 18 to 85 years of age, inclusive, at screening.

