6.2. Rescreening Criteria

Part 1 participants who are not enrolled within the screening period will be screen failed. Rescreening may be allowed after approval from the Medical Monitor. Participants who rescreen after the screening period must be reconsented with a new screening number, and the screening assessments must be repeated. The participant may not be required to repeat the MRI imaging or CSF screening assessment, if performed within 3 months prior to screening. Clinical outcome assessments performed within 8 weeks prior to screening may not be required to be repeated after approval from the Medical Monitor.

Those aFTD-GRN and FTD-GRN participants who have completed Study AL001-1 (described in [Section 1.2.2](#)) may enroll in this study. Participants must be rescreened after completion of Study AL001-1 and meet all inclusion/exclusion criteria applicable to this study. The participant may not be required to repeat the imaging (MRI) or CSF baseline assessment if performed within 3 months prior to screening. The participant may not be required to repeat the safety and tolerability assessments, if performed within 6 weeks prior to screening.

All participants are not required to report WGS results, and there is no time restriction for reporting.

Rescreening is not applicable for Part 2 of the study.

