Baseline will be defined as the last non-missing assessment, including repeated and unscheduled measurements, prior to the start of first study drug administration.

Due to the high rate of participant attrition over the study duration and small FTD cohort sizes, time points beyond week 49 will not be included in the cohort level summary of the figures.

All CIs will be 2-sided and performed using a 5% significance level except for PK parameters for which, 90% CI and geometric mean will be used. All p-values will be presented to 3 decimal places and values less than 0.001 or greater than 0.999 will be presented as <0.001 and >0.999, respectively. As the objectives of the study are exploratory in nature no adjustments for multiplicity will be made.

No formal significance testing will be performed.

Analysis visit windows will be applied for COA and Biomarker analysis. A detailed explanation about the analysis visit windows will be described in the specific section of each analysis,

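### Progranulin baseline is tied to the first AL001-2 dose, so in carriers already dosed in AL001-1 change from baseline can be understated by an amount nobody can judge

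*SAP*

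**What the plan says.** SAP section 2, in the same wording as protocol 8.4, states: "Baseline will be defined as the last non-missing assessment, including repeated and unscheduled measurements, prior to the start of first study drug administration". Three other places show that this means the first AL001-2 dose. SAP 5.3 makes the first dose date Study Day 1, SAP 10.1 assigns study days up to 1 to Baseline, and protocol Table 6 and SAP 8.1 place the first plasma PGRN sample at Week 1 before dosing. SAP 8.1 and 8.2 then present absolute and percent change in PGRN from that baseline.

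Some participants are not new to the drug. Protocol 3.1 admits asymptomatic carriers to the GRN cohort, "but only if they participated in the Phase 1 AL001-1 study". Symptomatic AL001-1 carriers may also enter once they have "Completed Study AL001-1 through the Day 57 visit" (protocol 4.1.1); for asymptomatic carriers the corresponding visit is Day 43. Converters are handled separately: "If a participant becomes symptomatic during or after Study AL001-1, they will be screened under Category 3 (symptomatic"). The title of Category 3 describes its members as new.

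There is one partial exception. SAP 10.2 takes baseline values from AL001-1 for an unnamed subset of CSF biomarkers, and only when the screening puncture was skipped because the AL001-1 baseline puncture fell within 3 months before screening. It does not say whether PGRN is included. There is no plasma equivalent, and no analysis uses or reports the time since the last AL001-1 dose.

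**The concern.** Change from baseline in plasma and in CSF PGRN are secondary endpoints. With the Sortilin assay dropped (SAP section 12), PGRN is the remaining named marker of target engagement. A baseline that is still drug-raised makes the change look smaller than it is.

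All of aFTD-GRN is exposed to this. FTD-GRN can mix exposed and unexposed participants, so its mean change has no single meaning. A participant who uses the SAP 10.2 exception could even have a pre-exposure CSF baseline and a post-exposure plasma baseline for the same protein. The error also enters the baseline-to-Week-49 correlations in SAP 10.4.

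Short gaps between studies are foreseen. Protocol 6.2 says of participants from AL001-1: "The participant may not be required to repeat the safety and tolerability assessments, if performed within 6 weeks prior to screening". The SAP 10.2 exception likewise presumes an AL001-1 baseline puncture within 3 months of screening.

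**Working it through.** The plan gives no figure on this point, so the inputs are the AL001-1 results in protocol 1.2.2.1.

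**1. Who is affected.** AL001-1 dosed 6 asymptomatic and 8 symptomatic carriers: 6 + 8 = 14 at most, against a GRN cap of 20 (14/20 = 70%). FTD-C9orf72 participants and truly new GRN carriers are unaffected.

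**2. Earliest rollover.**
- Asymptomatic: single dose on Day 1, so 43 − 1 = 42 days after dosing.
- Symptomatic: three doses two weeks apart, the last on Day 29, so 57 − 29 = 28 days after the last dose.

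**3. PGRN at that point.**
- Symptomatic plasma: "median concentrations of 93.7 to 97.6 ng/mL at Day 8 through Day 57 of the study", against an untreated mean of 31.7 ng/mL. The ratio is 93.7/31.7 = 2.96 to 97.6/31.7 = 3.08.
- Symptomatic CSF: 3.76 ng/mL, "approximately 1.2 times the baseline level of HV, assessed 28 days after the third dose of 30 mg/kg AL001", against an untreated 1.82 ng/mL. The ratio is 3.76/1.82 = 2.07.
- Healthy volunteers after 60 mg/kg, CSF: "42 days after dosing the PGRN level was increased 1.23-fold over baseline". This is the nearest proxy for asymptomatic carriers at Day 43.

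**4. Absolute change.** The understatement equals baseline minus untreated level, whatever the on-drug level. The upper bound, with baseline still at symptomatic Day 57 levels, is:
- plasma: 93.7 − 31.7 = 62.0 to 97.6 − 31.7 = 65.9 ng/mL (a median minus a mean);
- CSF: 3.76 − 1.82 = 1.94 ng/mL.

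If the on-drug plasma level is assumed to be 121 ng/mL (midpoint of the 118–124 reported for asymptomatic carriers), the true rise is 121 − 31.7 = 89.3 ng/mL. The loss is then 62.0/89.3 = 69% to 65.9/89.3 = 74% of the change. With full washout it is 0%.

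**5. Percent change.** If the baseline is R times the untreated level, reported % = (100 + true %)/R − 100. Illustrative values:

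| True rise | R = 1.1 | R = 1.5 | R = 2.0 |
|---|---|---|---|
| +200% | +173% | +100% | +50% |
| +300% | +264% | +167% | +100% |

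Plasma decay is not reported, so no day can be attached to these.

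**6. CSF excess over time.** One healthy-volunteer cohort was sampled at 24 days (1.83-fold) and 42 days (1.23-fold). The decay rate is k = ln(0.83/0.23)/18 = 0.0713 per day, a half-life of 9.7 days. Excess for aFTD-GRN is 0.23·exp(−k(d − 42)). For symptomatic carriers it is 1.066·exp(−k(d − 28)), which is weaker because the regimen differs. Brackets show half that rate as a stress test.

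| Days since last dose | aFTD-GRN | Symptomatic |
|---|---|---|
| 28 | – | 107% |
| 42 | 23% | – |
| 48 | 15% (19%) | 26% (52%) |
| 70 | 3% (8%) | 5% (24%) |
| 90 | 1% (4%) | 1% (12%) |

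**7. What limits the gap.** Exclusion criterion 25 exempts AL001-1 in its 30-day clause but does not repeat the exemption in its clause on biologics (90 days or 5 half-lives). If a 90-day gap to dosing applies, a CSF sample at the start of the 6-week screening period could fall at 90 − 42 = 48 days, and one near Day 1 at about 90.

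For anyone using the SAP 10.2 exception, take 3 months as 91 days and the reused puncture as pre-dose. Screening is then at most 91 days after the single dose, or 91 − 28 = 63 days after the third dose. Adding 42 days of screening puts the plasma baseline within 133 days (asymptomatic) or 105 days (symptomatic) of the last AL001-1 dose.

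**The case against.** The strongest reply is that a possibility is shown, not a bias. The documents do not say how long participants were off drug, and the 62.0–65.9 ng/mL ceiling needs a Week 1 sample at Day 57 levels even though rescreening comes first. On the central decay estimate the CSF effect is modest by 70 days. True rises of +125% (3.76/1.67) and +107% (3.76/1.82) would read about +118% and +96%, although the half-rate case gives about +67% for symptomatic carriers. That decay rests on two healthy-volunteer time points.

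Absolute PGRN is summarised, listed and plotted by individual. The stated pharmacological aim of restoring normal CSF levels is judged on absolute values. There is no formal testing, and any bias runs toward no effect. The 14 of 20 is a ratio of two ceilings, and one asymptomatic AL001-1 participant was incorrectly dosed. A within-study baseline also fits the 96-week objective, and splitting FTD-GRN makes small cells.

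All of this stands as a limit on size, but none of it supplies the missing rule. Absolute levels do not repair endpoints defined as change, and without the gap a reader cannot tell which values are affected.

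It could also be said that protocol 3.3.1 defines study drug as AL001, so the baseline rule might mean the first AL001 dose ever. The Study Day 1 definition and the sampling schedule point the other way, and no text brings AL001-1 plasma PGRN into the analysis. Either reading needs a sentence in the SAP.

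**Conclusion.** The concern holds. For up to 14 GRN carriers, including all of aFTD-GRN, the plasma PGRN baseline follows earlier AL001 exposure. The CSF baseline does too when the puncture is repeated. Change is understated by exactly the excess remaining at baseline. That excess lies between zero and, for symptomatic carriers at Day 57 levels, 62.0–65.9 ng/mL in plasma and 1.94 ng/mL in CSF. Where in that range the trial falls depends on an interval that is neither stated nor planned to be reported.

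The time-specific CSF figures assume that healthy-volunteer single-dose decay applies to carriers, including after three 30 mg/kg doses. They show a range and are not a forecast. The point should be fixed because a secondary endpoint is affected and the remedy uses data that already exist. Confidence is medium because the actual gaps are unknown.

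**What to change.** In SAP 8.1 and 8.2:
- For every participant with prior exposure, defined by actual AL001-1 dosing and not by enrolment category, summarise change and percent change in PGRN from the last value before the first AL001-1 dose, alongside change from the AL001-2 baseline.
- Split FTD-GRN PGRN summaries by prior exposure.
- Tabulate days from the last AL001-1 dose to each plasma and CSF baseline sample.

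In SAP 10.2, state whether CSF PGRN is among the biomarkers covered and that the AL001-1 puncture used is pre-dose.

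In SAP 10.4, keep the AL001-2 baseline for the Week 49 correlations so that intervals match the CDR plus NACC FTLD Sum of Boxes, and repeat them without previously exposed participants. This cannot be done for aFTD-GRN, where all are exposed; say so.

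The sponsor should reconcile the two clauses of exclusion criterion 25 as they apply to AL001-1.

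The cost is SAP wording, two extra summaries and transfer of existing AL001-1 PGRN data, which SAP 10.2 already plans for some CSF biomarkers. The downsides are possible assay-batch differences between studies and an off-treatment interval inside the longer change. Showing both baselines makes these visible.

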2.1. Sample Size

Part 1 (Treatment Period)

The primary objective of Part 1 of this study is to assess the safety profile of repeat dosing of AL001 in three FTD cohorts: aFTD-*GRN*, FTD-*GRN*, and FTD-*C9orf72* participants.

Descriptive statistics will be used to assess clinically significant associated findings (for example, study-drug related AEs leading to study drug discontinuation or study-drug related SAEs). The Part 1 sample size of 40 participants was chosen based on feasibility; however, the probability of detecting at least 1 clinically significant associated finding will be explored. When the probability of a clinically significant associated finding for a single participant is 0.1%, 1%, 5%, and 10%, then with a sample size of 40 participants, the probability of detecting at least

1 clinically significant associated finding across all participants is 3.9%, 33.1%, 87.1%, and 98.5%, respectively.

Part 2 (Optional OLE)

It is estimated that up to 40 participants from Part 1 of the study will be eligible to continue with Part 2 of the study. Part 2 is optional for participants, and at the discretion of the investigator.

2.2. Randomization and Blinding

This is an open label study where all participants will receive AL001, and doses are not concealed; randomization and blinding, therefore, are not required.

2.3. Analysis Populations

The following analysis sets will be used in the statistical analyses:

2.3.1. Enrolled Population

The enrolled population will consist of all participants who signed the ICF.

2.3.2. Safety Analysis Population

The safety analysis population will consist of all participants who received at least 1 dose of AL001. The safety analysis population will be used for all safety and COA summaries.

2.3.3. PK Analysis Population

The PK analysis population will include all participants in the safety population who had adequate assessments for determination of at least 1 PK parameter. The PK analysis population will be used for PK parameter summaries.

2.3.4. Full Analysis Population

The Full analysis population will include all participants in the safety population who had both a baseline and at least 1 postdose PD assessment. The Full analysis population will be used for summaries of all PD and PD biomarker summaries.

3. Participant Disposition and Protocol Deviations

3.1. Disposition

Participant disposition will be summarized. The number of participants and reasons for study discontinuation, reasons for study drug discontinuation, and the number of participants in each analysis population will be presented.

Participant disposition data and membership in analysis populations for participants in the Enrolled population will be presented in data listings.

Data collected for participants who failed screening will not be presented in any summaries or data listings.

3.2. Protocol Deviations

A protocol deviation occurs when the participant, investigator, or Alector (or designee) fails to adhere to protocol requirements. Major protocol deviations are the ones that affect the participants' safety or the primary endpoint (safety). Major protocol deviations for this study include, but are not limited to, the following:

- Failure to meet inclusion/exclusion criteria
- Failure to comply with GCP guidelines will also result in a major protocol deviation; Alector will determine if a major protocol deviation will result in withdrawal of a participant.

Major protocol deviations will be summarized for the Safety population, and all protocol deviations will be presented in a data listing, including the categorization of the deviation as major or minor.

4. Demographics and Baseline Characteristics

Qualitative data (eg, genotyping data, diagnostic characterization) will be summarized in contingency tables, and quantitative data (eg, age) will be summarized using quantitative descriptive statistics.

